11.2.1.2 Suspected Unexpected Serious Adverse Reaction (SUSAR) Definition

A SUSAR is any AE for which there is evidence to suggest a causal relationship between the drug and the AE, and which is assessed as both unexpected and serious. A suspected adverse reaction is considered “unexpected” if it is not listed in the Investigator’s Brochure or if it is not listed at the specificity or severity that has been observed. Expectedness will be determined by the Sponsor.

11.2.1.3 Non-serious AE Leading to Discontinuation

If situation permits, non-serious events (including laboratory abnormalities) that may require permanent discontinuation of study drug should be discussed with the Medical Expert prior to making any final decision, and if discontinued, should be entered on the eCRF within 3 working days.

11.2.2 Reporting

All initial and follow-up information regarding SAEs or SUSARs, including those related to protocol-mandated procedures and regardless of suspected causality, must be reported by the investigator immediately (within 24 hours of discovery) to the Sponsor and Premier Research. Reporting must not be delayed by waiting for additional information. **The minimum information required for reporting an SAE are the subject ID, the AE term (diagnosis) and the investigator’s initial assessment of causality.** Additional information can be reported to the Sponsor and Premier Research as a follow up report. Subjects will be provided investigator contact information for reporting SAEs.

In addition to telephone notification (discussed above), serious adverse event data must be entered on the Serious Adverse Event Report form and transmitted within 48 hours.

It is the responsibility of the Sponsor to assess expectedness. Premier Research’s responsibility is to report SUSARs to investigators, central IECs/IRBs/HRECs, national ethics committees if applicable, and appropriate Regulatory Authorities within the time frames required by applicable regulations. It is the investigator’s responsibility to notify the regional ethical or institutional review boards of SAEs and any new and significant safety information. At minimum, SUSARs must be brought to the attention of these review boards in accordance with regional regulations.

11.3. Event of Special Interest: Local Tolerability

An abnormal injection site reaction is defined as:

- An injection site reaction which is observed at the time of visit and is moderate to severe in intensity

- An injection site reaction between the previous and present visit, or remaining at the time of visit, which requires medical attention
- Any other injection site reaction deemed abnormal (eg, intensity and/or duration) to the investigator's judgment, other than those ordinarily observed in subcutaneous injections

Assessment of local tolerability will be performed by examining the injection sites (by the investigator if a reaction is present at the time of a visit) and on the basis of anamnestic data and records in the Subject Diary. At first study drug administration at Visit 1, local tolerability assessments will be done at 15 min, 1h and 2h postdose.

Observations will be recorded on appropriate eCRF pages. If an injection site reaction meets the criteria defined for an "abnormal result" it will be considered an AE.

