10.1.2.1 TransCon hGH Cohort (Cohort 1)

- Visits 1 and 2 will be performed on the day of the 1st and 5th dosing (Days 1 and 29), respectively.
- Visits 3, 4 and 5 will be performed 48-72 hours after the 13th, 26th and 39th dose, respectively.
- Visit 6 will be performed 7 days after the last dose (Day 365).

All attempts should be made to adhere to the planned visit schedule. However, in case the subject is not able to attend Visits 3, 4, 5 and 6 during Week 13, 26, 39 or 52, respectively, these visits can be performed with a + 2 week window for Visit 3, meaning either Week 14 or 15, if Week 13 is not achievable; and a ± 1 week window for Visits 4, and 5, meaning either Week 25 or 27, if Week 26 is not achievable or Week 38 or 40, if Week 39 is not achievable; and a + 1 week visit window for Visit 6, meaning Week 53, if Week 52 is not achievable.

Bioanalytical sampling will follow in accordance with the Schedule of Events ([Attachment 17.2](#)). All visits should be in the morning for consistency of auxology measurements, and because subjects should be fasting for Visits 1, 4, and 6.

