10.1.2.2 Genotropin Cohort (Cohort 2)

- At Visit 1, subjects will be dosed in the morning at the clinic.
- All subjects in the Genotropin cohort will attend Visit 1 fasting with administration of the dose at the investigational site and predose sampling, and will have an additional postdose sampling for hGH at 2 hours.

- Visits 2, 3, 4 and 5 will be performed on any day during Weeks 5, 13, 26 and 39, respectively. Preferably, all clinic visits will be in the morning for consistency of auxology measurements. Visit 4 needs to be conducted in the morning hours, since the subject is requested to be fasting. Visit 6 will be performed 1 day after the last dosing (Day 365) in the morning hours, since the subject is requested to be fasting.

All attempts should be made to adhere to the planned visit schedule. However, in case the subject is not able to attend Visit 3, 4, 5 and 6 during Week 13, 26, 39, or 52, respectively, these visits can be performed with a + 2 week window for Visit 3, meaning either Week 14 or Week 15, if Week 13 is not achievable; and a ± 1 week visit window for Visits 4 and 5, meaning either Week 25 or 27, if Week 26 is not achievable or Week 38 or 40, if Week 39 is not achievable; and a + 1 week visit window for Visit 6, meaning Week 53, if Week 52 is not achievable. Visit assessments can occur on any day during the concerned Weeks 5, 13, 26, 39, and 52 in accordance with the Schedule of Events ([Attachment 17.3](#)).

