10.3. Assessments

10.3.1 Safety and Efficacy

Safety and efficacy assessments will be performed throughout the trial. All samples obtained after Informed Consent will be shipped to a selected central laboratory for analysis. Safety samples may be analyzed locally in case of emergency or if logistics or other unforeseen events do not permit a central analysis. During visits where study drug administration is planned at the site, these assessments will be performed prior to such administration (predose). While fasting is recommended for all visits, fasting is required at Visits 1, 4, and 6. The following procedures will be performed during V1 through V6 unless otherwise indicated:

- 1) Physical examination and vital sign measurement (blood pressure, heart rate, body temperature, respiratory rate) (subjects should rest for at least 5 minutes before vital sign assessment)

- 2) Review of concomitant medication
- 3) Review of Subject Diary by investigator (V2-V6)
- 4) Evaluation of AEs and local tolerability
- 5) Safety assessments:
 - Hormone levels {TSH, fT4, fT3, and morning cortisol; V1 (fasting), V3, V4 (fasting) and V6 (fasting)}
 - Routine safety biochemistry parameters (sodium, potassium, calcium, phosphate, chloride, total bilirubin, alkaline phosphatase, LDH, AST, ALT, GGT, albumin, total protein, creatinine, urea-nitrogen, uric acid, serum iron and transferrin)
 - Hematology parameters (hemoglobin, leukocytes, differential blood count of leukocytes, platelet count; blood smears will be performed locally for back-up analysis, if needed)
 - Parameters of glucose metabolism: fasting glucose (when required), insulin, and HbA1c (glucose metabolism parameters can be assessed locally at any time if there is suspicion of impaired glucose tolerance, which may include an OGTT)
 - Parameters of lipid metabolism (cholesterol, LDL and HDL, and triglycerides)
- 6) Immunogenicity assessment: anti-hGH and anti-PEG antibodies (Cohort 2: anti-PEG antibodies only at Screening and V1 predose, in support of trial specific assay cut-point determination); a subject with observed anti-hGH binding antibodies post dosing (V3-V5) at or close to the C_{max} for TransCon hGH may be brought back for a repeat sample to assess for neutralizing antibodies at a time point deemed appropriate to exclude assay interference. Anti-PEG antibodies will only be analyzed at the end of the individual treatment period once all samples from an individual subject are available.

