14.3.4 Other Safety Data Summary Tables

Table 14.3.4.1	SAFETY	Summary of Vital Signs by Visit
Table 14.3.4.2	SAFETY	Summary of Electrocardiogram (ECG) Assessment by Visit
Table 14.3.4.3	SAFETY	Summary of Electrocardiogram (ECG) Data by Visit
Table 14.3.4.4	SAFETY	Electrocardiogram (ECG) Data: Shift in Assessments Compared to Baseline
Table 14.3.4.5	SAFETY	Summary of Bone Age
Table 14.3.4.6	SAFETY	Physical Examination Results by Body System and Visit
Table 14.3.4.7	SAFETY	Pubertal Status: Summary Assessment by Sex and Visit
Table 14.3.4.8.1	SAFETY	Local Tolerability from Site by Visit: Summary of Subjects with Injection Related Events
Table 14.3.4.8.2	SAFETY	Local Tolerability from Site by Visit and Severity: Summary of Subjects with Injection Related Events
Table 14.3.4.8.3	SAFETY	Local Tolerability from Site by Maximum Severity and Symptom for Overall Study: Summary of Subjects with Injection Related Events
Table 14.3.4.8.4.1	SAFETY	Local Tolerability from Patient Diary by Week - TransCon hGH: Summary of Subjects with Injection Related Events
Table 14.3.4.8.4.2	SAFETY	Local Tolerability from Patient Diary by Day - Genotropin: Summary of Subjects with Injection Related Events
Table 14.3.4.8.5.1	SAFETY	Local Tolerability from Patient Diary by Week and Severity - TransCon hGH: Summary of Subjects with Injection Related Events
Table 14.3.4.8.5.2	SAFETY	Local Tolerability from Patient Diary by Day and Severity - Genotropin: Summary of Subjects with Injection Related Events
Table 14.3.4.8.6	SAFETY	Local Tolerability from Patient Diary by Maximum Severity and Symptom for Overall Study: Summary of Subjects with Injection Related Events
Table 14.3.4.8.7	SAFETY	Exposure Adjusted Local Tolerability from Patient Diary for Overall Study
Table 14.3.4.8.8	SAFETY	Exposure Adjusted Local Tolerability from Patient Diary by Severity for Overall Study
Table 14.3.4.9	SAFETY	Concomitant Medication: Incidences by ATC Level 2 and 4
Table 14.3.4.10.1	SAFETY	Exposure to Study Treatment and Compliance
Table 14.3.4.10.2.1	SAFETY	Exposure to Study Treatment by Week – TransCon hGH
Table 14.3.4.10.2.2	SAFETY	Exposure to Study Treatment by Day – Genotropin
Table 14.3.4.10.3	SAFETY	Summary of Dose Timings
Table 14.3.4.10.4	SAFETY	Weight-based Planned Dosage (mg/dose) by Visit
Table 14.3.4.11	SAFETY	Serum concentration by Visit and PK analytes
Table 14.3.4.12	PK	Serum Concentration by Time Point and PK analytes at Visit: Individual data including Summary Statistics

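### After Visit 1, the at-visit AE rule for moderate or severe injection-site reactions applies at different times since dosing in the two arms and may favour TransCon

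*Protocol*

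**What the plan says.** Protocol 11.3 defines an abnormal injection-site reaction in three bullets and treats any reaction that meets one of them as an AE.

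- First bullet: "An injection site reaction which is observed at the time of visit and is moderate to severe in intensity".
- Second bullet: "An injection site reaction between the previous and present visit, or remaining at the time of visit, which requires medical attention".
- Third bullet: any other reaction that the investigator judges abnormal, with intensity and duration named as possible grounds.

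The assessment rests on examination and also "on the basis of anamnestic data and records in the Subject Diary". Both arms are examined at 15 min, 1 h and 2 h after the first dose at Visit 1. Protocol 10.1.2.3 adds checks at 15 min, 1 h, 2 h and 24 h after dose 13 in the TransCon PK/PD subset (at least 8 subjects).

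The visit schedule differs by arm:

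- **TransCon** (Protocol 10.1.2.1): Visit 2 is on the day of dose 5, and under 10.3.1 its assessments come before that dose. "Visits 3, 4 and 5 will be performed 48-72 hours after the 13th, 26th and 39th dose, respectively". Visit 6 is 7 days after the last dose.
- **Genotropin** (Protocol 9.3.2 and 10.1.2.2): dosing is daily, recommended at bedtime. Visits 2 to 5 may be on any day of the scheduled week, preferably in the morning. "Visit 6 will be performed 1 day after the last dosing (Day 365) in the morning hours".

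The SAP (list 14.3.4) plans site-examined tables, for example "Local Tolerability from Site by Visit and Severity: Summary of Subjects with Injection Related Events", and separate diary tables. Two of the diary tables, 14.3.4.8.7 and 14.3.4.8.8, are exposure-adjusted.

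**The concern.** The first bullet is the only automatic route that turns on severity, and it requires the reaction to be seen at the visit. The second bullet reaches back between visits, but only for reactions needing medical attention. A moderate or severe reaction at home that fades unaided is left to the third bullet, which is a judgement made by an investigator who knows the treatment.

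That would matter little if both arms were seen at similar times after dosing. They are not. From Visit 2 on, TransCon subjects are examined days after an injection and Genotropin subjects within about a day. A short-lived reaction can therefore be visible at a Genotropin visit and gone by a TransCon visit. Protocol 5.3 describes phase 2 injection-site reactions as generally mild and transient, and short duration is what makes the timing matter.

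Local tolerability is the protocol's named event of special interest and a listed safety endpoint, as is AE incidence. At stake is a between-arm comparison of injection-site AEs that could look better for the test product partly because of when the children are seen.

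**Working it through.** **Step 1. Reproduce the visit timing.** Weekly dose k falls on Day 1 + 7(k − 1), so doses 13, 26, 39 and 52 fall on Days 85, 176, 267 and 358. Adding 48-72 h gives Days 87-88, 178-179 and 269-270; 358 + 7 = 365. These match Table 2 of Protocol 10.1.2. For Visit 2, dose 4 is on Day 22, and 29 − 22 = 7 days = 168 h.

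**Step 2. Time since last injection.**

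| Visit | TransCon | Genotropin |
|---|---|---|
| 2 | 168 h | about 12-24 h |
| 3, 4, 5 | 48-72 h | about 12-24 h |
| 6 | 164-172 h | up to about 24 h |

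The Genotropin hours are inferred from bedtime or morning home dosing and morning visits. It follows that, outside the PK/PD subset, a reaction to a home TransCon injection lasting under 48 h cannot meet the first bullet at a scheduled Visit 2 to 6. A Genotropin reaction lasting 12 to 24 h can.

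**Step 3. Share of all reactions captured by the first bullet at Visits 2 to 6.** The documents give no reaction duration. Assume exponential durations with mean m, an equal chance of reaction at every injection, 52 weekly or 364 daily injections, TransCon visits at 60 h (three) and 168 h (two), and Genotropin visits at 20 h (five). Summing over all earlier injections:

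- TransCon = [3·exp(−60/m) + 2·exp(−168/m)] / [1 − exp(−168/m)] / 52
- Genotropin = 5·exp(−20/m) / [1 − exp(−24/m)] / 364

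For m = 24 h:

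- TransCon: (3 × 0.0821 + 2 × 0.0009) / 0.9991 / 52 = 0.48%
- Genotropin: 5 × 0.4346 / 0.6321 / 364 = 0.94%

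| Mean duration (assumed) | TransCon | Genotropin | Ratio |
|---|---|---|---|
| 12 h | 0.04% | 0.30% | 0.13 |
| 24 h | 0.48% | 0.94% | 0.51 |
| 48 h | 1.8% | 2.3% | 0.79 |

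**Step 4. Is the ratio due to timing or to injection frequency?** If visits fell at random points in the dosing cycle, the expected share would be 5·m/(168 × 52) for TransCon and 5·m/(24 × 364) for Genotropin. Both denominators are 8,736, so the ratio would be 1. The departure from 1 comes from visit timing.

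**Step 5. Sensitivity to the Genotropin gap.** With 12 h in place of 20 h, Genotropin capture is 0.58%, 1.3% and 2.7% (ratios 0.07, 0.36 and 0.67). With 24 h it is 0.21%, 0.80% and 2.1% (ratios 0.18, 0.60 and 0.86). The direction does not change.

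**The case against.** **Faded reactions are not simply lost.** A reader might infer that a moderate or severe reaction can be an AE only if it is still visible. The documents do not support that. The second bullet makes a resolved reaction an AE automatically if it needed medical attention, and the third lets the investigator act on history or the diary. Protocol 11.3.2 has families guided to record reactions and queried at visits, with intensity, onset and end date captured. This narrows the gap to reactions that resolved without medical attention. It does not close it, because the remaining route is an unblinded judgement.

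**Some observation opportunities favour TransCon capture.** TransCon is injected on site at Visit 2 and Genotropin is not. Protocol 11.3.1 has staff rate pain when an injection is given at the site. The PK/PD subset is followed to 24 h after dose 13 and receives dose 14 in clinic. These points stand. However, the schedule sets no post-dose injection-site time points at Visit 2, and the subset is small.

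**The last-injection figures overstate the size.** With a 24 h mean, a reaction to the last injection before a visit is still present with probability exp(−20/24) = 43% on Genotropin, against exp(−60/24) = 8% or exp(−168/24) = 0.1% on TransCon. A reader might take that contrast as the size of the undercount. It is not, because most injections are not followed by a visit. Over all injections the criterion misses most reactions in both arms.

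**The SAP already plans diary tables.** SAP 9.9 summarises site and family assessments whatever the AE status, and AE summaries carry no inferential tests. This softens the point. But the diary tables leave the AE counts unchanged, neither document names them as the between-arm comparison, and SAP 9.8 does not say which source its injection-site reaction counts use.

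The grading scale in Appendix 2 is redacted, so any timing instruction in it cannot be seen.

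**Conclusion.** The concern holds in a limited form. Outside Visit 1 and the PK/PD subset at Visit 3, automatic AE status for a moderate or severe reaction that needs no medical attention depends on a visit at 48 to 168 h after dosing on TransCon and about 24 h or less on Genotropin. Injection-site AE counts, and site-examined Tables 14.3.4.8.1 to 14.3.4.8.3 after Visit 1, may therefore be biased in favour of TransCon.

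The schedule fixes the direction for the first bullet. The size rests on assumed durations: with Genotropin visits at 20 h, TransCon capture per reaction is about 0.13, 0.51 or 0.79 of Genotropin capture for means of 12, 24 or 48 h. How far the third bullet offsets this cannot be known from the documents. They do not support saying that the rule certainly lowers the TransCon count, or that reactions go unrecorded, since the diary collects them in both arms.

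**What to change.** In Protocol 11.3, change the first bullet to: *An injection site reaction of moderate or severe intensity observed at the visit or recorded in the Subject Diary since the previous visit*, applied identically in both arms.

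In SAP 9.8/9.9, name the diary tables, including the exposure-adjusted ones (14.3.4.8.6 to 14.3.4.8.8), as the basis of the between-arm local-tolerability comparison. Footnote the site-examined tables after Visit 1 as not comparable between arms because time since dosing differs.

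The cost is one protocol sentence and a short SAP addition. No new data are needed, since intensity and dates are already captured. The SAP part can be done from collected data even if follow-up is complete.

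The downside is more non-serious injection-site AEs in both arms. A reader might expect the increase mainly on TransCon, but that is unsupported: Genotropin has 364/52 = 7 times as many injections, and the current first bullet misses most of its reactions too, so the increase may be larger there. AE counts should therefore be read alongside the exposure-adjusted diary tables.

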11.3.1 Injection Site Pain

Injection site pain will be evaluated by the investigator or designated staff if the injection is given at the clinical site and by the parent/legal guardian if the injection is given at home. The pain will be evaluated using the Wong-Baker FACES Pain Rating Scale (see [Appendix 2](#)). In addition, each subject and parent/legal guardian will be queried during visits regarding possible injection site pain.

11.3.2 Injection Site Status

Injection site status will be evaluated by the investigator or designated staff using the Injection Site Assessment Scale ([Appendix 2](#)). In addition, each subject and parent/legal guardian will be guided to record possible reactions in the Subject Diary and will be queried during visits.

The following information will be captured:

- Description of the reaction
- Location: left thigh/right thigh/left buttock/right buttock/left part of abdomen/right part of abdomen
- Duration: onset, end date
- Intensity: grading according to the scales provided in appendices (the investigator should assess the subjects/subject's parents/legal guardians description)
- Action taken: action(s) taken by subjects, medical intervention or medication
- Comments

12. SAFETY MONITORING

The Sponsor will conduct an ongoing review of all trial data, with particular attention given to laboratory findings, AEs, and concomitant medication data. Any significant trends in safety observations or other findings of significance that are considered related to study drug will be reported to the investigators and to Regulatory Authorities. In particular, the Sponsor will notify investigators and Regulatory Authorities of AEs that:

- Are serious in nature and not commonly seen in the absence of exposure to somatropin
- Occur at a greater frequency or at greater severity than described in the current Investigator's Brochure for TransCon hGH for Injection

Any AE that occurs in the course of the clinical trial must be monitored and followed up until:

- It has receded
- Pathological laboratory findings have returned to normal
- Steady state has been achieved
- It has been shown to be unrelated to the study drug and/or trial related procedures

It is the responsibility of the investigator to ensure that any necessary additional therapeutic measures and follow-up procedures are performed.

13. STATISTICS

The SAP will provide a detailed description of the planned statistical analyses. If discrepancies exist between the text of the statistical analysis as planned in the protocol and the final SAP, the final SAP will define the planned analysis of record.

13.1. Trial Endpoints

13.1.1 Primary Efficacy Endpoint

- Annualized HV at 52 weeks for weekly TransCon hGH and daily hGH treatment groups

13.1.2 Secondary Efficacy Endpoints

- Annualized HV for the TransCon hGH and the daily hGH treatment group over 52 weeks
- Change in HT SDS over 52 weeks for the TransCon hGH and the daily hGH treatment group
- Serum IGF-1 and IGFBP-3 levels and IGF-1 SDS and IGFBP-3 SDS; and the normalization of IGF-1 SDS over 52 weeks for the TransCon hGH and the daily hGH treatment group

13.1.3 Safety Endpoints

- Incidence of AEs
- Local tolerability (assessed by the subject, the parents/legal guardians and the investigator)
- Incidence of anti-hGH antibodies including neutralizing antibodies as needed (both cohorts) and incidence of treatment-emergent anti-PEG antibody formation (in TransCon hGH subjects)

- IGF-1 levels and IGF-1 SDS
- Parameters of glucose metabolism (fasting glucose and insulin level, HbA1c) and lipid parameters
- Hormone levels: thyroid status and morning cortisol
- All other hematology and biochemistry blood parameters
- ECG
- Results of the physical examinations, vital sign measurements
- Bone age at 52 weeks

